8.4 Withdrawal of Consent

Patients may withdraw or be withdrawn from the trial at any time without prejudice. In the event of consent withdrawal, patients will be asked for their permission to use the data already collected to date. If this permission is declined, then any data collected to date on that patient will not be entered into the trial analysis.

If the patient and/or PI request termination of the trial drug during the treatment period, the drug will be stopped and the patient will revert to standard care treatment. The patient will be advised that if any event occurs within 28 days of receiving the last dose of the study drug, which the patient considers might be related to the study drug, the patient should contact the clinic to discuss with the PI.

As an additional safeguard, the PI or designee will contact the patient by telephone 4 weeks post study drug termination to assess if the patient has experienced any adverse events.

If a patient withdraws or is withdrawn from the trial they will be offered the standard care treatment which is currently anti VEGF drugs within the National Health Service (NHS).

Withdrawal of consent, or patient/PI request to terminate the study drug, will be recorded on the Case Report Form (CRF).

9. STUDY DRUG

9.1 Study Drug Description

ARA 290 is an 11-amino acid peptide derived from the spatial configuration of the external face of helix B of the protein erythropoietin. ARA 290 is a novel, first-in-class activator-peptide of the Innate Repair Receptor (IRR) that antagonises inflammation and tissue injury and promotes endogenous repair mechanisms. ARA 290 is an anti-inflammatory agent that has an effect in preventing the death of cells. As inflammation is known to play a role in the occurrence of DMO it could potentially be helpful in treating patients with this condition. The ARA 290 drug product used for subcutaneous injection is provided as aseptic vials containing 5.6 mg ARA 290, which after reconstitution with 0.66 mL sterile Water for Injection, contains a solution of 8 mg/mL ARA 290 in a 20 mM sodium phosphate buffer, pH 6.5, containing 1% sucrose and 4% D-mannitol. A volume of 0.5 mL contains 4 mg ARA 290.

9.2 Study Drug Supply

As described in the IMPD, Patheon Italia S.P.A. [name] and PCI, [name] are responsible for manufacture, QP release, import and shipment of ARA290.

Study drug packs will be packaged and labelled by Victoria Pharmaceuticals, [name] in compliance with applicable regulatory requirements.

Study drug packs will be dispatched to the responsible pharmacist at the participating site under the instruction of the Trial Manager.

Each patient will be given an initial pack containing 30 vials of study drug. Replacement packs of 30 vials will be provided at visits as required, to a maximum of 3 packs x 30 vials.

Each pack will provide enough study drug for 28 days treatment (with 2 days of study drug overage to allow for the drug spilling or spoiling, and to provide a +/- 2 day window around study visits).

9.3 Study Drug Accountability

The hospital pharmacy will maintain accurate records of all Investigational Medicinal Product (IMP) received (including date of receipt, batch numbers, expiry date, quantities of drug shipments), dispensed and returned on the Drug Accountability Log. Records must be available to the study monitors on request. Patients will be asked to return used and unused vials of study drug to the site at each study visit as applicable. Unallocated, unused and used study drug will be destroyed at site with permission from the CTU and in accordance with site pharmacy procedure for destruction of IMP and hospital waste management policies. A record of the destruction will be maintained.

9.4 Study Drug Storage

The study drug will be stored in BHSCT Pharmacy under refrigerated conditions at 2-8°C When a study pack is dispensed to a patient, the patient will be advised to store this in their home refrigerator.

9.5 Study Drug Administration

After giving consent and being recruited on to the study, the patient's baseline assessment will be carried out and recorded.

The first subcutaneous injection of ARA 290 at a dose of 4 mg will be self-administered by the patient at the first patient visit. The patient will receive practical instructions on how to self-administer the drug. The patient will be required to remain at the site for one hour after the first administration for observation. Any adverse events will be recorded in the CRF. The patient will self-administer subsequent 4 mg subcutaneous injections for the 84 day study drug period unless there is reason for discontinuation of the study drug.

Study medications should be injected subcutaneously in the front or side of the thigh daily, in the morning. Patients are advised to rotate daily injection sites to avoid injecting into the same area repeatedly. In the unlikely event that the patient is unable to inject into the thigh they may inject into the abdomen.

The patient will be provided with Study Drug Administration Guidelines to instruct them how to reconstitute the study drug for injection and how to administer the injection. The patient will also be provided with a Study Drug Diary Card and will be instructed to note each daily study drug administered.

The PI or designee should confirm that all study drugs are administered as per protocol by checking the returned Study Drug Diary Card. Any anomalies in study drug used/unused will be queried with the patient and in the event that the patient has not administered study drug, this will be recorded as a protocol deviation in the CRF.

The completed Study Drug Diary Card should be filed alongside the patient CRF.

9.6 Study Drug Termination

The study drug will be discontinued if any of the following conditions are met prior to the study drug treatment period of 12 weeks:

- 1. Patient or clinician request for withdrawal from the study.
- 2. Patients whose sight is determined as deteriorating to the point of a 10 letter drop in sight. The study drug will be stopped and the patient will be offered the current standard care treatment.

Whilst on the study enrolled participants, [i.e. patients with DMO and thick retinas (400 microns or more)] will be receiving the study drug rather than the current standard treatment (currently anti VEGF drugs in the NHS). Patients who wish to withdraw from the study, those in whom sight loss occurs during the duration of the study or those completing the study in who DMO persists, will be offered this standard care treatment.

10. PARTICIPANT TIMELINE: SCHEDULE OF ASSESSMENT AND DATA COLLECTION

10.1 Schedule of Assessments

All patients must be evaluated during the study according to the schedule of assessments outlined in Table 2.

Table 2: Schedule of Assessments

	Screening/ Baseline	2 weeks	4 weeks	8 weeks	12 weeks	16 weeks*	4 weeks post drug termination**
Consent	✓						
Pregnancy Test	√						
Medical History	✓		√	✓	√	✓	
Medications	✓		✓	√	√	✓	
Vital Signs***	✓		✓	√	✓	√	
Distance Visual Acuity	✓		✓	✓	✓	✓	
Microperimetry	 ✓ 				✓	✓	
Schirmer Test	✓				✓	✓	
SD-OCT	 ✓ 		✓	✓	✓	✓	
Wide-angle FFA	✓				✓		
Blood sample for ARA 290 antibodies, immune markers, carbamylated and glycosylated albumin	✓				✓		
Blood sample for full blood cell count	√				√	√	
Liver function test (LFT)	 ✓ 				~	✓	
Urine Sample	✓				✓	✓	
Adverse Events		~	~	~	~	✓	✓
VFQ-25	~				~	✓	
EQ-5D-5L	 ✓ 				~	✓	
C-SSRS	~		~	√	~	✓	
Telephone check		✓					 ✓

* 16 week visit will take place only if the retina is found to be dried and the DMO has resolved at week 12

** 4 week post study drug termination telephone check will be completed for patients who withdraw from the trial/study drug prior to 12 weeks, or at 12 weeks, and who do not need to attend the 16 week visit.

 *** Vital signs: height (first visit only); weight; heart rate; temperature; blood pressure, oxygen saturation, BMI

10.2 Best Corrected Distance Visual Acuity

Best corrected distance visual acuity will be obtained in both eyes by a trained optometrist using the Early Treatment Diabetic Retinopathy Study (ETDRS) charts at baseline and at weeks 4, 8 and 12. If at week 12 the retina is dry, a further visit at week 16 will be undertaken and BCVA will be obtained at this visit. The EDTRS total score will be recorded and used for the analysis.

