5. STUDY DESIGN

5.1 Study Design

A prospective, open label, interventional, single centre, investigator led, phase II study to examine the effect of ARA 290 on diabetic macular oedema in patients with type 1 or 2 diabetes.

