6. OUTCOME MEASURES

6.1 Primary Outcome Measure

Changes from baseline to week 12 (+/- 7 days) in best corrected distance visual acuity.

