7.5 Allocation Concealment Mechanism

This will be an open label study thus the Principal Investigator (PI) and patients will not be masked to study treatment.

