10.4 Retinal Perfusion, as Determined by Fundus Fluorescein Angiography

Retinal perfusion will be assessed by wide angle fundus fluorescein angiography (FFA). Wideangle fluorescein angiographic images will be obtained by an ophthalmic photographer with the help of a research nurse at baseline and at the week 12 visit. The FFA run will be obtained from the study eye; images in the fellow eye will also be obtained at arterio-venous and later phases of the angiogram.

Wide angle FFA results will be evaluated qualitatively for the presence/absence and extension of areas of retinal ischaemia. The FFA obtained at the 12 week follow up visit will be compared with that obtained at baseline to determine the existence of new areas of ischaemia and the increased/reduced size of pre-existing areas of ischaemia.

In addition it is planned that areas of retinal ischaemia will also be detected and quantified automatically using an ImageJ program developed by our group. This software uses a combination of four binary masks, calculated independently, to adapt the detection of ischemic areas to different regions of the image. Images will be evaluated by an investigator masked to the participant and the study visit. Total area of ischaemia will be determined and used for the analysis.

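### In a single-arm, open-label trial, neither the BCVA examiner nor the qualitative angiogram reading is shielded from earlier results, so examiner or reader expectation would pass straight into the change estimates.

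*Protocol*

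**What the plan says.** The primary outcome is given as "Changes from baseline to week 12 (+/- 7 days) in best corrected distance visual acuity" (Protocol 6.1). Protocol 10.2 names the examiner ("Best corrected distance visual acuity will be obtained in both eyes by a trained optometrist") and the measure: "The EDTRS total score will be recorded and used for the analysis". The BCVA definition in SAP section 4 repeats this.

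The design is "A prospective, open label, interventional, single centre, investigator led, phase II study to examine the effect of ARA 290" (Protocol 5.1). There is one treated group of ten and no comparator (Protocol 12.1). On masking, Protocol 7.5 says that "the Principal Investigator (PI) and patients will not be masked to study treatment"; it does not mention the optometrist.

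BCVA and SD-OCT fall at the same visits (Protocol Table 2). The OCT is taken by a photographer (Protocol 10.3). The only rule on test order puts the Schirmer test after BCVA and microperimetry (Protocol 10.6); it does not mention OCT.

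Protocol 10.4 describes two readings of the angiograms. The qualitative one is introduced with "Wide angle FFA results will be evaluated qualitatively for the presence/absence and extension of areas of retinal ischaemia", followed by a direct comparison of week 12 with baseline. The quantitative one uses automated software, and that paragraph contains the masking statement: "Images will be evaluated by an investigator masked to the participant and the study visit".

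**The concern.** A letter score depends on how hard the patient tries and on how the examiner encourages, waits and scores. That is general measurement knowledge, not a statement in the documents. Because every patient is treated, masking to treatment has no meaning here. What can be masked is the visit, the earlier scores and the scan, and for the primary outcome the plan does none of these.

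In a controlled trial, drift common to both arms would cancel. Here nothing cancels it, and the two responder outcomes (gains of at least 10 and at least 15 letters) rest on the same score. Protocol 3.3 argues that improvement could most likely be credited to ARA 290 because spontaneous resolution is improbable. That argument covers the natural history of the oedema, not how the score is taken.

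The qualitative angiogram reading has the same weakness. It supplies the macular, foveal and peripheral rows of SAP Table 3.1, where change is classed as extension, reduction or no change. A reader who knows which image is later can lean towards one of these.

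**Working it through.** **1. Which assessments are shielded?**

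| Assessment | Who | Stated protection |
|---|---|---|
| BCVA (primary) | optometrist | none stated on visit, earlier scores or OCT |
| Qualitative angiogram reading | not named | none stated; week 12 compared with baseline |
| Automated ischaemia area | investigator | masked to participant and visit |

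The plan therefore already accepts visit masking and has someone to do it, but states it only for the automated measure.

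**2. How large could the effect be?** The plan has no figure to reproduce: ten patients are justified without an effect size, an SD or an error rate (Protocol 12.1, SAP section 5). What follows is an illustration.

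Inputs:
- n = 10, from the documents.
- Interval level 95%: assumed. SAP section 6 promises confidence intervals but gives no level.
- SD of change s = 6, 8 or 10 letters: assumed.
- Mean drift b = 2 or 3 letters, with zero drug effect: assumed.

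Half-width = t × s/√n, with t = 2.262 on 9 degrees of freedom. For s = 8 this is 2.262 × 8/3.162 = 5.72 letters.

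The chance that the lower limit exceeds zero is the probability that a noncentral t variable (9 df, noncentrality b√n/s) exceeds 2.262. For b = 2 and s = 8 the noncentrality is 2 × 3.162/8 = 0.791 and the probability is 10.6%.

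| SD of change | Half-width | No drift | Drift 2 letters | Drift 3 letters |
|---|---|---|---|---|
| 6 | 4.29 | 2.5% | 15.5% | 29.3% |
| 8 | 5.72 | 2.5% | 10.6% | 18.5% |
| 10 | 7.15 | 2.5% | 8.2% | 13.4% |

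**3. Responder outcome.** Take a normally distributed change with SD 8 and count a score above 9.5 as a gain of at least 10 letters. The expected share is 1 − Φ((9.5 − b)/8): 12% with no drift, 17% with 2 letters and 21% with 3.

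**4. What does not depend on the assumptions.** With one arm, expected mean change = drug effect + drift + other non-drug change. Drift enters with coefficient 1, whatever the SD or sample size.

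**5. Can it still be changed?** SAP section 6 records that no patient needed a week-16 visit. That visit depends on the retina being dry at week 12, so BCVA collection was probably complete when the SAP was written. Angiograms, if stored, can still be re-read.

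**The case against.** **The gap is inferred from silence.** Protocol 7.2 says that procedures for the listed equipment, which includes the ETDRS charts, come with a training manual that is not among these documents. It may restrict access to scores or fix the test order, and the OCT is already in other hands. This stands. A reader might infer that the optometrist does see earlier scores and scans; the documents neither permit nor forbid it. If a rule exists, one sentence in Protocol 10.2 would settle the matter.

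**The plan makes no decision that drift could overturn.** The analysis is descriptive, with no test or success criterion. This also stands: a reader might take 8% to 29% for the trial's false-positive rate, but the plan has no rule based on an interval lying above zero. Yet descriptive means are biased by drift too, and the primary objective is to determine whether the drug benefits BCVA.

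**Masking the examiner would not deal with expectation as a whole.** Correct. Patients are unmasked, and practice effects and regression to the mean remain; removing these needs a concurrent control.

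**The masking sentence in 10.4 may be meant for both angiogram readings.** Its position in the automated paragraph does not show this, and a direct comparison with baseline is masked only if the order is hidden.

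**The qualitative reading may not stand alone.** A reader might infer that it would be the only perfusion result, since SAP section 6 allows the perfusion image analysis to be deferred. The SAP does not say which analysis it means, and deferral to a later report is not loss.

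**Worsening is foreseen too.** Protocol 9.6 provides for a 10-letter loss, so the documents do not support saying that every later score is expected to be better. In addition, central subfield thickness, which depends less on patient effort, is reported beside BCVA.

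**Conclusion.** The concern holds as a gap in protection against examiner and reader expectation. It does not show that bias occurred. The documents establish a single unmasked arm, a letter-score primary outcome with no stated shielding of its examiner, an unmasked qualitative comparison of angiograms, and visit masking stated only for the automated area. With no control arm, any such expectation enters the change estimates in full.

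Its size cannot be derived from the documents. The 8% to 29% range rests on an assumed drift of 2 to 3 letters, an SD of 6 to 10 letters, a 95% level and zero drug effect. It shows sensitivity, not an expected error. Nor would better masking by itself make a BCVA gain attributable to ARA 290.

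The change is worth making, but its weight is tempered by the declared pilot purpose and descriptive analysis. The angiogram part can probably still be corrected; the BCVA part may be left as a limitation to report.

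**What to change.** 1. **Angiograms (Protocol 10.4, SAP section 4).** Let the masked investigator already planned for the area images also make the qualitative reading. Present each patient's baseline and week-12 sets in random order, and assign extension, reduction or no change only after the order is revealed. Stored images allow this now. The cost is removing dates from the images, preparing the random order and some reading time.

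2. **BCVA still to be collected (Protocol 10.2).** At each visit, test BCVA before OCT, with the optometrist having no access to earlier letter scores, OCT images or the visit record. The investigator can still compare scores for the discontinuation criterion in Protocol 9.6. Staff and tests are unchanged.

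3. **BCVA already collected.** Report what the optometrist could see and in what order the tests were done, citing the training manual if it sets a rule. State examiner expectation as a limit on crediting the change to ARA 290. Do not write a masking procedure into the SAP after the event as though it had been followed.

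Downsides: earlier scores must be kept out of the examination room, and the masking is partial. A patient may mention the visit, and microperimetry, also done by an optometrist, takes place only at baseline, week 12 and any week 16, so it can reveal the visit. Patient expectation, practice effects and regression to the mean are untouched and belong in the same limitation statement.

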10.3 Central Subfield Retinal Thickness

Central subfield retinal thickness (CST), as obtained in the central 1 mm area, will be determined by spectral domain optical coherence tomography (SD-OCT) and used for the analysis. In addition, presence or absence of intraretinal or subretinal fluid will be evaluated and recorded in the appropriate CRF. SD-OCT will be obtained in both eyes by an ophthalmic photographer at baseline and weeks 4, 8 and 12. If at week 12 the retina is dry, a further visit at week 16 will be undertaken and SD-OCT obtained at this visit.

10.4 Retinal Perfusion, as Determined by Fundus Fluorescein Angiography

Retinal perfusion will be assessed by wide angle fundus fluorescein angiography (FFA). Wideangle fluorescein angiographic images will be obtained by an ophthalmic photographer with the help of a research nurse at baseline and at the week 12 visit. The FFA run will be obtained from the study eye; images in the fellow eye will also be obtained at arterio-venous and later phases of the angiogram.

Wide angle FFA results will be evaluated qualitatively for the presence/absence and extension of areas of retinal ischaemia. The FFA obtained at the 12 week follow up visit will be compared with that obtained at baseline to determine the existence of new areas of ischaemia and the increased/reduced size of pre-existing areas of ischaemia.

In addition it is planned that areas of retinal ischaemia will also be detected and quantified automatically using an ImageJ program developed by our group. This software uses a combination of four binary masks, calculated independently, to adapt the detection of ischemic areas to different regions of the image. Images will be evaluated by an investigator masked to the participant and the study visit. Total area of ischaemia will be determined and used for the analysis.

10.5 Macular Function, as Determined by Macular Microperimetry

Retinal sensitivity will be determined by macular microperimetry in both eyes. Microperimetry will be undertaken by an optometrist at baseline and at 12 weeks. If at week 12 the retina is dry, a further visit at week 16 will be undertaken and macular microperimetry obtained.

Mean sensitivity in the central 10 degrees of the retina will be recorded and used for the analysis.

10.6 Schirmer Test

The Schirmer test will be performed to measure tear production. The test will be undertaken by a Research Nurse at baseline and at week 12. If a further visit at week 16 is undertaken, this test will be also performed at this additional visit. This is a safe test which poses no risk to the patient. A negative test result is normal i.e. more than 10mm of moisture on the filter paper in 5 minutes. As both eyes normally secrete the same amount of tears, this test will be only done in the study eye (see Statistical Considerations section). This test will be done following completion of all functional tests (i.e. BCVA and microperimetry). This test is included as patients with DR often complain of dry eyes, most likely related to reduced corneal nerve fibre density. Given the effect of ARA 290 in increasing corneal nerve terminals observed in previous studies, we plan to evaluate whether tear film production may improve following this treatment. The millimetres of moisture on the filter paper for each eye will be recorded and used for the analysis

10.7 Patient Reported Outcomes

Patient reported outcomes will be evaluated by means of EQ-5D 5L and NEI VFQ-25 questionnaires which will be administered to patients at baseline and at week 12 (and at week 16 if applicable). The NEI VFQ-25 is a vision specific patient reported quality of life tool. This validated questionnaire has been used widely to evaluate visual outcomes in patients with eye diseases including DR. In addition to eliciting information about general health and vision it specifically addresses difficulty with near vision, distance vision, driving and the effect of light conditions on vision. This provides a comprehensive evaluation of vision related quality of life. A generic health status measure EQ-5D-5L will be used to generate utility data. Total scores will be recorded and used for the analysis. Suicidal ideation will be assessed using the Columbia Suicide Severity Rating Scale (C-SSRS) which will be administered to patients at baseline and weeks 4, 8 and 12. If at 12 weeks the retina is dry a further visit at week 16 will be arranged and questionnaires completed.

All outcomes will be recorded in CRFs or questionnaires specifically designed for the study.

